#### 1.44 Safety considerations from DC therapy

DC vaccine therapy clinical trials in B-cell NHL have thus far demonstrated no significant adverse events or autoimmunity (Table 1). DC immunotherapy has been used for many different tumors types where adverse events (such as induced autoimmunity) were monitored. Importantly, very few significant adverse effects of DC vaccination have been reported and DC immunotherapy clinical trials performed to date have shown no evidence of resultant generation of autoimmunity. To date, 86 patients have been treated with DC therapy without any serious drug related toxicity reported. In our trial LS1081, 15 patients were treated without any autoimmunity or grade 3 or higher adverse events attributable to treatments. The most common adverse event was injection site pain, more often with cryoablation, that usually resolved within 2 days of treatments (Table 2).

Table 1. Summary of clinical trials using dendritic cell vaccines for NHL

Histopath Diagnosis	Phase (N)	Ag source	DC source	Delivery	Safety	Clinical outcome
Follicular (Hsu, Benike et al. 1996)	I (4)	Idiotype	Blood *	IV	No Grade 3-4 AEs; no AI	1 CR, 1 PR, 1 molecular CR
Follicular (Timmerman, Czerwinski et al. 2002)	I (10) II (25)	Idiotype	Blood *	IV	No Grade 3-4 AEs; no AI	I: 3 CR, 1 PR, 6 PD II: 16 CR, 7 PR, 2 PD
Follicular, lymphoplasmacytoid (Di Nicola, Zappasodi et al. 2009)	I (18)	Heat-shocked autologous tumor cells	Matured from monocytes	SC	No Grade 3-4 AEs; no AI	3 CR, 3 PR, 8 SD, 4 PD
Follicular (Kolstad, 2015)	I (14)	in situ loading via intra-tumor injection	Immature DC from monocytes	Intra-tumor	No Grade 3-4 AEs; No AI	2 CR, 3 PR
Indolent B-cell NHL (LS1081 preliminary results)	I (Arm A: 10; Arm B: 5)	Arm A: in situ via intra-tumor injections Arm B: tumor lysate	Matured from monocytes	Arm A: intra-tumor Arm B: intradermal	No Grade 3-4 AEs; no AI	Arm A: 5 PR Arm B: 1 CR, 2 PR

Blood-derived DC used gradient centrifugation and adhesion method. DCs were characterized by negative phenotype markers without description of maturation markers normally used in release criteria. (AI = autoimmunity. CR = complete remission. IV = intravenous. PD = progressive disease. PR = partial remission. SC = subcutaneous. SD = stable disease.)

Table 2. Summary of adverse events attributable to treatments in LS1081 study

[figure not shown]
Adverse Event		Grade							
		1		2		3		4	
Type	Arm	N	%	N	%	N	%	N	%
Urticaria	A	2	25.0	1	12.5				
Bronchospasm	A			1	12.5				
Injection site reaction	A			1	12.5				
Lymph node pain	A			1	12.5				
Rash maculo-papular	A			1	12.5				
Vasovagal reaction	A					1	12.5		

Grade 3 vasovagal reaction was due to line placement for leukopheresis prior to active vaccine

treatment. Reaction resolved with IV fluids and reverse Trendelenburg maneuver.

### 1.5 Rationale for pneumococcal conjugate vaccine (PCV) therapy

We have found that, compared to healthy donors, NHL patients have significantly decreased number of lymphocytes, particularly CD4+ cells (Lin, Gustafson et al. 2011). This combined with the *in vitro* suppressed immune function argue for T cell stimulation to augment immune response with DC vaccine. PCV (Pevnar®) is approved by the US Food and Drug Administration for vaccination against pneumococcal infections in children and works by activating helper T cells to interact with B cells for antibody production (Pletz, Maus et al. 2008). Pneumococcal vaccination has been shown to be safe and recommended for cancer patients that will or have undergone chemotherapy (Melcher 2005). Thus, the use of pneumococcal vaccines presents little if any additional risk to the patient. The use of these vaccines does allow determination of the state of the immune system and its response to the DC based vaccines. Pevnar has been used in two clinical trials for multiple myeloma patients in this manner. These trials included one with adoptive T cell transfer after stem cell transplant (Rapoport, Stadtmauer et al. 2005) and another with lenalidomide (Noonan et al. ASH Annual Meeting 2008, Blood abstract 2772). Both trials reported minimal toxicity. In addition there may be a bystander effect on immunity with enhanced lymphocyte trafficking and the response to one antigen leading to enhanced response to anti-tumor antigens (Mitchell, Batich et al. 2015). Preliminary study in our lab showed that Pevnar enhanced mature DC stimulated CD4 T cell proliferation by approximately 1.75 fold compared to mature DC stimulation alone (Figure 1). Importantly, a review of the results of DC therapy in melanoma suggest that addition of adjuvant capable of T cell help, significantly improved overall clinical response (Engell-Noerregaard, Hansen et al. 2009, Mitchell, Batich et al. 2015). We are including this vaccine to enable us to monitor the immune response prior to and after our intervention. The vaccine will also allow us to quantify any potential *in vivo* bystander effect due to the combination of DC and pneumococcal vaccine. In the LS1081 study, no adverse events were seen with Pevnar administrations.

**Figure 1. CD4+ T cell proliferation is stimulated with mature dendritic cells pulsed with Pevnar.** Monocyte-depleted PBMNC from healthy donors were labeled with CFSE and cultured for 7 days without stimulation or with Pevnar, autologous mature dendritic cells (mDC), or autologous mDC pulsed with Pevnar. At the end of culture, cells were stained with 7-AAD, anti-CD3 and anti-CD4 and analyzed by flow cytometry. Percent of live, CD4 T cells that proliferated are shown here for 3 donors. CD4 T cell proliferation was the greatest in co-culture with Pevnar-pulsed mDC.

#### 1.51 Safety considerations for the use of 13-valent pneumococcal conjugate vaccine (PCV) therapy

PCV (Pevnar®) is approved by the US Food and Drug Administration for vaccination against pneumococcal infections in children and works by activating helper T cells to interact with B cells for antibody production (Pletz, Maus et al.

2008). Pneumococcal vaccination is considered safe for cancer patients undergoing chemotherapy with mild side effects including soreness, low-grade fever and induration at the site of vaccination lasting 1-3 days (Melcher 2005). It has been used in two clinical trials for multiple myeloma patients, one with adoptive T cell transfer after stem cell transplant (Rapoport, Stadtmauer et al. 2005) and another with lenalidomide (Noonan et al. ASH Annual Meeting 2008, Blood Abstract #2772). Both trials reported minimal toxicity and some evidence of improved immune response. As in Rapoport et al, we will use this pneumococcal vaccine to evaluate and monitor the developing immune response. The proposed Prevnar13 (Prevnar) dosing schedule in this study is similar to the Prevnar schedule in LS1081 study. No significant toxicities were observed in 15 patients who received Prevnar along with their DC vaccines. We will use the dose administration and timing as approved for use (Prevnar product insert; [REDACTED])

## 1.6 Cryoablation therapy

[figure not shown]
### 1.61 Cryoablation background

Percutaneous cryoablation systems are currently available from two manufacturers including Endocare, Incorporated (Irvine, CA) and Galil Medical (St. Paul, MN), each are FDA 510K cleared for treatment of soft-tissue tumors. Since 2003, investigators in this study have used cryoablation for the treatment of renal, lung, soft tissue, and bone tumors, including treatment of patients enrolled in the LS1081 study. Probes may be placed either percutaneously or intraoperatively using US or CT image guidance.

The mechanism of cryoablation is based on delivery of argon gas through a segmentally insulated probe with outer diameter ranging from 1.7 – 2.4 mm, with expansion of the gas within the probe lumen, resulting in rapid cooling (via Joule Thompson effect). With expansion of the argon gas within the probe, rapid and extreme temperature drops are produced along the distal, uninsulated probe shaft reaching –100 °C within a few seconds. Adjacent tissues are quickly frozen, resulting in the formation of an iceball. Thawing of the iceball is achieved with active instillation of helium gas into the cryoprobes instead of argon gas.

Cell death is due to two primary causes. First, rapid freezing immediately adjacent to the probe results in intracellular ice formation, organelle disruption, and subsequent cell destruction. At a further distance from the probe, relative gradual cooling causes osmotic differences across the cell membrane with secondary cellular dehydration and death. Subsequently, further cell death occurs due to thrombosis of affected blood vessels and resultant ischemic necrosis.

The size of the iceball varies depending on the length of uninsulated tip, with commonly used cryoprobes generating an iceball of about 3 cm in diameter and 5 cm in longitudinal length along the probe shaft. The growth and size of the iceball can be controlled by the delivery system through the relative amount of argon passed through the cryoprobe. Given relative cellular tolerance to freezing temperatures, cell death occurs within about 3-5 mm internal to the iceball margin (Campbell, Krishnamurthi et al. 1998; Chosy, Nakada et al. 1998). A target lesion is typically treated with curative intent using two freezing cycles of approximately 10 minutes each, separated by a 5-minute thaw period (Figure 2).

**Figure 2. Example of lymphoma tumor cryoablation.** Low grade follicular lymphoma lesion involving the left kidney (left panel yellow circle) can be seen before and during the course of cryoablation (middle panel). The probe used for cryoablation is indicated by the white arrow and the growing ice ball identified by the red arrows. The size and predictability of the growth of the ice ball is independent of the tumor source. Right panel shows resolution of the lesion after treatment.

#### 1.62 Safety considerations for cryoablation

Outside of the liver, complications due to cryoablation are primarily related to inadvertent tissue injury at the ablation site. A large experience exists regarding percutaneous cryoablation of renal tumors, showing a major complication rate of 5-8% (Silverman, Tuncali et al. 2005, Littrup, Ahmed et al. 2007, Atwell, Farrell et al. 2008, Atwell, Carter et al. 2012). Similar to RFA, the majority of complications are related to local tissue trauma, including hemorrhage in about 3% of patients. Allowing for a more limited published experience, complications following bone and soft tissue ablation are even more infrequent, ranging from 0-2% (Beland, Dupuy et al. 2005, Ullrick, Hebert et al. 2008, Callstrom, Dupuy et al. 2013). Unique to cryoablation, compared to RFA, is the ability to visualize the cytotoxic ice develop using CT imaging, allow the user to precisely control the volume of tissue treated and minimize adjacent tissue injury (Figure 2).

Of particular note, a systemic phenomenon called “cryoshock” has been observed primarily in the cryoablation of liver tumors. Cryoshock is clinically manifested by severe coagulopathy, disseminated intravascular coagulation, and multiorgan failure, possibly related to a systemic inflammatory response syndrome. This syndrome has been seen in about 1% of cases of hepatic cryotherapy and only 0.04% of prostate cryoablations (Seifert and Morris 1999). We have used clinical cryoablation alone to treat a limited number of patients with lymphomatous tumor masses with no serious safety issues identified. In the LS1081 study, no cryoshock or  $\geq$ Grade 3 adverse events were observed with cryoablation treatments (Table 1).

#### 1.7 This Study and Research Hypothesis

This study is a phase I/II design where the phase I portion will confirm the starting dose and regimen of the phase II portion (which is expected to be dose level 1) and the phase II portion will receive the same regimen as determined by the phase I portion. The patient population in the phase II portion is patients with Non-Hodgkin lymphoma. Given the evidence of PD-1 and its ligands expression in neoplastic lymphoma cells, the

tumor microenvironment, and systemically, we hypothesize that PD-1 blockade combined with DC vaccine will enhance DC priming of T cells with anti-tumor antigen and activate T cell functions. The combined immunotherapy with pembrolizumab, cryoablation followed by intra-tumor injection of DC vaccines will generate anti-tumor immunity and clinical regression of lymphoma.

## **2.0 Goals**

### **2.1 Phase I**

#### **2.11 Primary**

Evaluate the optimal dose schedule, safety and tolerability as measured by the incidence of significant toxicity of combination therapy with anti-PD-1 monoclonal antibody, cryoablation, and intra-tumor injection of autologous dendritic cell into the cryoablated tumor.

#### **2.12 Secondary**

2.121 Evaluate the feasibility of this combination immunotherapy.

2.122 Evaluate patient quality of life

### **2.2 Phase II**

#### **2.21 Primary**

Test the efficacy (overall response rate) of combination therapy with anti-PD-1 monoclonal antibody, cryoablation, and intra-tumor injection of autologous dendritic cell vaccine.

#### **2.22 Secondary**

2.221 Evaluate the PR and CR rate of this combination immunotherapy.

2.222 Evaluate the progression free survival, treatment free survival, duration of response, disease-free rate at 2 years, and overall survival of this combination immunotherapy.

2.223 Evaluate the safety of this combination immunotherapy.

#### **2.23 Correlative Studies**

2.231 Assess the effect of combination immunotherapy on patients' immune status and anti-tumor immune response.

2.232 Assess the potential association between PD-1/PD-L1/PD-L2 expression in tumor and blood with clinical efficacy.

2.233 Assess the potential association between tumor antigen mutations and antigen-specific immune response with clinical efficacy.

2.234 Evaluate patient quality of life.

### 3.0 Patient Eligibility

#### 3.1 Inclusion Criteria

- 3.11 Age  $\geq 18$  years.
- 3.12 Histological confirmation of biopsy-proven non-Hodgkin lymphoma, *excluding* chronic lymphocytic leukemia, primary CNS lymphoma and Burkitt's lymphoma.  
Note: Small lymphocytic lymphoma (SLL) is allowed.
- 3.13 Patients with indolent NHL must have had  $\geq 1$  regimen of rituximab-containing regimen.  
Note: This includes FL, marginal lymphoma and MALT.
- 3.14 Patients with aggressive NHL must have had  $\geq 2$  regimens.  
Note: This includes DLBCL, MCL, PMBCL, and T cell lymphoma.
- Patients with aggressive NHL must have received prior therapy – at a minimum:
- Anti-CD20 monoclonal antibody unless tumor is CD20 negative and
  - An anthracycline containing regimen.
  - Transformed FL must have had therapy for FL and be refractory to chemotherapy for DLBCL.
- Chemotherapy refractory disease in aggressive NHL is defined as
- Stable disease of  $\leq 12$  months or progressive disease as best response to most recent chemotherapy containing regimen.
  - Disease progression or recurrence  $\leq 12$  months of prior autologous SCT.
- Patients with aggressive NHL must have failed autologous HSCT, or are ineligible or not consenting to autologous HSCT.
- 3.15 Patient must have at least 3 measurable lesions that are  $\geq 1.5$  cm in one dimension. One of the lesions must be  $\geq 2.0$  cm and is amenable to image-guided cryoablation and multiple vaccine injections as determined by Interventional Radiology and PI (including tumors that can be safely accessed using imaging guidance and treated with minimal risk to adjacent structures).
- 3.16 ECOG Performance Status (PS) 0 or 1 (Appendix I).
- 3.17 The following laboratory values obtained  $\leq 14$  days prior to registration.
- Absolute neutrophil count (ANC)  $\geq 1000/\text{mm}^3$
  - Absolute lymphocyte count  $\geq 200/\text{mm}^3$
  - Platelet count  $\geq 50,000/\text{mm}^3$
  - Hemoglobin  $\geq 8.0$  g/dL
  - Total bilirubin  $\leq 1.5$  x upper limit of normal (ULN), unless due to Gilbert's disease.
  - Aspartate transaminase (AST/SGOT) and alanine transaminase (ALT/SGPT)  $\leq 2.5$  x ULN
  - Creatinine  $\leq 1.5$  x ULN or calculated creatinine clearance  $\geq 60$  mL/min for subject with creatinine  $> 1.5$  x institutional ULN
- 3.18 Negative serum pregnancy test for women of childbearing potential  $\leq 7$  days prior to registration.  
Note: A second pregnancy test may be required  $\leq 72$  hours prior to receiving the first dose of study medication.

- 3.19a Negative human immunodeficiency virus (HIV), hepatitis B and C, and tuberculosis (TB) test.
- 3.19b Provide written informed consent.
- 3.19c Willing to return to the enrolling institution for follow-up (during active treatment and active monitoring phase of the study).
- 3.19d Ability to complete questionnaire(s) by themselves or with assistance.
- 3.19e Willing to provide tissue and blood samples for research purposes (see Sections 6.0, 14.0 and 17.0).
- 3.19f Willing to use adequate contraception as defined in Section 9.0 while on the study and until 120 days after the last dose of study drug.
- 3.2 Exclusion Criteria
- 3.21 Any of the following because this study involves an investigational agent whose genotoxic, mutagenic and teratogenic effects on the developing fetus and newborn are unknown:
- Pregnant women
  - Nursing women
- 3.22 Co-morbid systemic illnesses or other severe concurrent disease which, in the judgment of the investigator, would make the patient inappropriate for entry into this study or interfere significantly with the proper assessment of safety and toxicity of the prescribed regimens.
- 3.23 Serious non-malignant disease such as active infection, symptomatic congestive heart failure, unstable angina pectoris, cardiac arrhythmia, or psychiatric illness/social situations or other conditions which in the opinion of the investigator would compromise protocol objectives.
- 3.24 Currently receiving or have received any other **investigational** agent considered as a treatment for the primary neoplasm  $\leq 28$  days or within 4 half-lives (whichever is shorter) of the agent prior to registration.
- 3.25 History of other primary malignancy requiring systemic treatment within 6 months of protocol enrollment.  
Patients must not be receiving chemotherapy or immunotherapy for another cancer. Patients must not have another active malignancy requiring active treatment with the following acceptable EXCEPTIONS:
- Basal cell carcinoma, squamous cell carcinoma, or melanoma of the skin that has undergone or will undergo potentially curative therapy
  - In situ cervical cancer that has undergone or will undergo potentially curative therapy
- 3.26 Prior allogeneic bone marrow or peripheral blood stem cell transplantation.
- 3.27 Prior autologous bone marrow or peripheral blood stem cell transplantation  $\leq 100$  days prior to registration or if recovery from the transplant is inadequate.
- 3.28 Major surgery other than diagnostic surgery  $\leq 4$  weeks prior to registration.
- 3.29a Prior chemotherapy or radiation therapy  $\leq 2$  weeks prior to registration or who has not recovered (i.e. to  $\leq$ Grade 1 or baseline) from an adverse event due to the previously administered therapy.

- 3.29b History of hypersensitivity and anaphylactoid reactions to pneumococcal vaccine or any component of the formulation, including diphtheria toxoid.
- 3.29c Active autoimmune disease such as Crohn's disease, rheumatoid arthritis, Sjögrens' disease, systemic lupus erythematosus, or similar conditions requiring systemic treatment within the past 3 months or a documented history of clinically severe autoimmune disease/syndrome difficult to control in the past.  
EXCEPTIONS:
- Vitiligo or resolved childhood asthma/atopy
  - Intermittent use of bronchodilators or local steroid injections
  - Hypothyroidism stable on hormone replacement,
  - Diabetes stable with current management
  - History of positive Coombs test but no evidence of hemolysis
  - Psoriasis not requiring systemic treatment
  - Conditions not expected to recur in the absence of an external trigger
- 3.29d Coagulopathy, including the use of Coumadin or heparin anticoagulants that cannot be discontinued for the cryoablation procedure. NOTE: Heparin for line patency without detectable lab abnormalities for coagulation will be allowed.
- 3.29e Corticosteroid use  $\leq 2$  weeks prior to registration.  
NOTE: Patients must be off corticosteroids for at least 2 weeks prior to registration. This includes oral, IV, subcutaneous, or inhaled route of administration. Patients on chronic corticosteroid for adrenal insufficiency or other reasons may enroll if they receive less than 10 mg/day of prednisone (or equivalent).
- 3.29f Active CNS malignancy.
- 3.29g Evidence of interstitial lung disease or active, non-infectious pneumonitis.
- 3.29h Received a live vaccine  $\leq 30$  days prior to registration.
- 3.29i New York Heart Association Classification III or IV cardiovascular disease (Appendix II) or recent myocardial infarction or unstable angina pectoris or cardiac arrhythmia  $\leq 30$  days prior to registration.

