## 11.0 Treatment Evaluation

**NOTE:** For assessment of index (target) and non-target lesions on whole body scan performed after completion of DC treatment, the baseline whole body scan will be used to assess overall treatment response of index (target) and non-target lesions. Include up to 6 index (target) lesions as measurable disease when assessing overall clinical response. The treatment lesion(s) is the lesion(s) that is cryoablated. This treatment lesion will be measured only at baseline and will not be included in assessment of overall clinical response, and will not be followed or measured.

**NOTE:** Subject(s) with progressive disease on anti-PD-1 monoclonal antibody alone prior to receiving cryoablation and intra-tumor injection of autologous DC will be continued on treatment to assess clinical response with the addition of these therapy as long as the provider and the investigator deemed clinically safe and reasonable.

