### 11.2 Lugano Classification Response criteria (Cheson, Fisher et al. 2014)

	PET-CT Based Response	CT-Based Response
Complete Response	Complete metabolic response (CMR)	Complete radiologic response (CR) (all of the following)
Lymph nodes and extralymphatic sites	Score 1, 2, or 3* with or without a residual mass on SPS† It is recognized that in Waldeyer's ring or extranodal sites with high physiologic uptake or with activation	Target nodes/nodal masses must regress to $\leq 1.5$ cm in LDi No extralymphatic sites of disease

	PET-CT Based Response	CT-Based Response
	within spleen or marrow (eg, with chemotherapy or myeloid colony-stimulating factors), uptake may be greater than normal mediastinum and/or liver. In this circumstance, complete metabolic response may be inferred if uptake at sites of initial involvement is no greater than surrounding normal tissue even if the tissue has high physiologic uptake	
Nonmeasured lesion	Not applicable	Absent
Organ enlargement	Not applicable	Regress to normal
New lesions	None	None
Bone marrow	No evidence of FDG-avid disease in marrow	Normal by morphology; if indeterminate, IHC negative
Partial Response	Partial metabolic response (PMR)	Partial remission (PR) (all of the following)
Lymph nodes and extralymphatic sites	Score 4 or 5† with reduced uptake compared with baseline and residual mass(es) of any size At interim, these findings suggest responding disease At end of treatment, these findings indicate residual disease	≥50% decrease in SPD of up to 6 target measurable nodes and extranodal sites When a lesion is too small to measure on CT, assign 0.5 cm X 0.5 cm as the default value When no longer visible, 0.0 X 0.0 cm For a node >0.5 cm X 0.5 cm, but smaller than normal, use actual measurement for calculation
Nonmeasured lesions	Not applicable	Absent/normal, regressed, but no increase
Organ enlargement	Not applicable	Spleen must have regressed by >50% in length beyond normal
New lesions	None	None
Bone marrow	Residual uptake higher than uptake in normal marrow but reduced compared with baseline (diffuse uptake compatible with reactive changes from chemotherapy allowed). If there are persistent focal changes in the marrow in the context of a nodal response, consideration should be given to further evaluation with MRI or biopsy or an interval scan	Not Applicable

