#### 11.21 Complete Response (CR).

The designation of CR requires all of the following:

- 11.211 Complete disappearance of all detectable clinical evidence of disease and definitely disease-related symptoms if present before therapy.
- 11.212 All lymph nodes and nodal masses must have regressed on CT to normal size ( $\leq 1.5$  cm in their greatest transverse diameter for nodes  $> 1.5$  cm before therapy). Previously involved nodes that were 1.1 to 1.5 cm in their long axis and more than 1.0 cm in their short axis before treatment must have decreased to  $\leq 1.0$  cm in their short axis after treatment.
- 11.213 The spleen and/or liver, if considered enlarged before therapy on the basis of a physical examination or CT scan, should not be palpable on physical examination and should be considered normal size by imaging studies, and nodules related to lymphoma should disappear. However, determination of splenic involvement is not always reliable because a spleen considered normal in size may still contain lymphoma, whereas an enlarged spleen may reflect variations in anatomy, blood volume, the use of hematopoietic growth factors, or causes other than lymphoma. Similarly, other organs considered to be enlarged before therapy due to involvement by lymphoma, such as liver and kidneys, must have decreased in size.

11.214 If the bone marrow was involved by lymphoma before treatment, the infiltrate must have cleared on repeat bone marrow biopsy. The biopsy sample on which this determination is made must be adequate (with a goal of >20 mm unilateral core). If the sample is indeterminate by morphology, it should be negative by immunohistochemistry. A sample that is negative by immunohistochemistry but that demonstrates a small population of clonal lymphocytes by flow cytometry will be considered a CR until data become available demonstrating a clear difference in patient outcome.

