#### 11.22 Criteria for Partial Response (PR)

The designation of PR requires all of the following:

11.221 At least a 50% decrease in sum of the product of the diameters (SPD) of up to six of the largest dominant nodes or nodal masses. These nodes or masses should be selected according to all of the following:

- they should be clearly measurable in at least 2 perpendicular dimensions
- if possible they should be from disparate regions of the body
- they should include mediastinal and retroperitoneal areas of disease whenever these sites are involved

11.222 No increase should be observed in the size of other nodes, liver, or spleen.

11.223 Splenic and hepatic nodules must regress by  $\geq 50\%$  in their SPD or, for single nodules, in the greatest transverse diameter.

11.224 With the exception of splenic and hepatic nodules, involvement of other organs is usually assessable and no measurable disease should be present.

11.225 Bone marrow assessment is irrelevant for determination of a PR if the sample was positive before treatment. However, if positive, the cell type should be specified (eg, large-cell lymphoma or small neoplastic B cells). Patients who achieve a CR by the above criteria, but who have persistent morphologic bone marrow involvement will be considered partial responders.

When the bone marrow was involved before therapy and a clinical CR was achieved, but with no bone marrow assessment after treatment, patients should be considered partial responders.

11.226 No new sites of disease should be observed.

11.227 CT criteria should be used.

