#### 11.24 Relapsed Disease (after CR)/Progressive Disease (after PR, SD)

Lymph nodes should be considered abnormal if the long axis is more than 1.5 cm regardless of the short axis. If a lymph node has a long axis of 1.1 to 1.5 cm, it should only be considered abnormal if its short axis is more than 1.0. Lymph nodes  $\leq 1.0 \times \leq 1.0$  cm will not be considered as abnormal for relapse or progressive disease.

- 11.241 Appearance of any new lesion more than 1.5 cm in any axis during or at the end of therapy, even if other lesions are decreasing in size. Increased FDG uptake in a previously unaffected site should only be considered relapsed or progressive disease after confirmation with other modalities. In patients with no prior history of pulmonary lymphoma, new lung nodules identified by CT are mostly benign. Thus, a therapeutic decision should not be made solely on the basis of the PET without histologic confirmation.
- 11.242 At least a 50% increase from nadir in the SPD of any previously involved nodes, or in a single involved node, or the size of other lesions (eg, splenic or hepatic nodules). To be considered progressive disease, a lymph node with a diameter of the short axis of less than 1.0 cm must increase by 50% and to a size of 1.5 x 1.5 cm or more than 1.5 cm in the long axis.
- 11.243 At least a 50% increase in the longest diameter of any single previously identified node more than 1 cm in its short axis.
- 11.244 Transformation to a more aggressive histology that requires a change in active treatment will be considered progressive disease.

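### The entry size floor for the lesions that count toward response (1.5 cm) equals the CT node-size limit for complete response, so in node-only disease read by CT alone that one component can be met at baseline

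*Combined protocol and SAP*

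**What the plan says.** **Entry.** Section 3.15 states "Patient must have at least 3 measurable lesions that are" 1.5 cm or more in one dimension. It sets no short-axis minimum. One lesion must be at least 2.0 "cm and is amenable to image-guided cryoablation and multiple vaccine injections".

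**Assessment.** Section 11.0 says the cryoablated lesion "will not be included in assessment of overall clinical response, and will not be followed or measured". Up to six other lesions serve as index (target) lesions.

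**Complete response by CT.** Table 11.2: "Target nodes/nodal masses must regress to" 1.5 cm or less in longest diameter, with no extralymphatic disease. The table gives no short-axis condition. Section 11.212 says "All lymph nodes and nodal masses must have regressed on CT to normal size", defined as 1.5 cm or less for nodes that began above 1.5 cm. It adds that nodes 1.1 to 1.5 cm long with a short axis above 1.0 cm before treatment must fall to 1.0 cm or less in the short axis.

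**Abnormal node.** Section 11.24 calls a node abnormal above 1.5 cm in the long axis. For smaller nodes the short axis decides, with a threshold of 1.0 cm: "If a lymph node has a long axis of 1.1 to 1.5 cm, it should only be considered abnormal if its short axis is more".

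**Partial response.** Table 11.2 and Section 11.221 require a fall of at least 50% in the sum of products of diameters (SPD). Of the nodes chosen, Section 11.221 says "they should be clearly measurable in at least 2 perpendicular dimensions".

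**Imaging.** Sections 4.1 and 16.41 allow CT or PET/CT. Section 11.1 allows either at baseline but also states that response is PET/CT-based.

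**Decision.** Success is PR or CR (16.3211). The regimen is promising with 13 or more responses in 28 (16.312).

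**The concern.** An entry criterion should guarantee disease that is abnormal on the scale later used to judge response. Here the guaranteed assessable disease is two lesions whose permitted minimum equals the maximum allowed for a complete responder. The only lesion required to be larger does not count.

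The primary endpoint is a single-arm response rate compared with a fixed 30%. There is no control arm in which the same misclassification would also occur, so any patient credited with response for nodes that were already small pushes the estimate upward. The CR rate, a secondary goal (2.221), is exposed in the same way.

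**Working it through.** **1. The plan's own figure.** Exact binomial, n = 28, success at 13 or more (inputs from 16.31 to 16.314):
- P(X >= 13 | 0.30) = 0.0491
- P(X >= 13 | 0.53) = 0.8122

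The stated 81% power and 0.05 type I error reproduce. There is almost no slack below 0.05.

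**2. Nodes that 3.15 admits, tested against the size rules.** SPD is long axis x short axis; with two equal nodes the percentage change is the same.

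| Node, before to after (cm) | SPD change | Table 11.2 CR size | 11.212 size | After: abnormal by 11.24? |
|---|---|---|---|---|
| 1.5 x 0.9, unchanged | 0% | met | no further demand | no |
| 1.5 x 1.2, unchanged | 0% | met | not met | yes |
| 1.6 x 1.2 to 1.5 x 1.2 | 1.92 to 1.80, -6% | met | met | yes |
| 1.8 x 1.2 to 1.5 x 1.1 | 2.16 to 1.65, -24% | met | met | yes |

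Row 1 is the overlap: the node is eligible, not abnormal by 11.24, and inside the CR size limit with no change.

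Row 2 shows that the rules disagree on the short axis. Table 11.2 accepts the node; 11.212 and 11.24 do not.

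Rows 3 and 4 show that the CR size limit can be reached with far less than the 50% fall needed for PR. These nodes begin above 1.5 cm, so they follow from the adopted CR rule and not from the entry floor. Their end states are also still abnormal by 11.24.

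**3. Size per patient.** 1/28 = 3.6 percentage points. If one of the 28 were certain to be counted a success and the other 27 each responded with probability 0.30, the chance of declaring the regimen promising would be P(X >= 12 of 27) = 0.080.

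**4. Illustration under an assumption.** Let f be the share of true non-responders counted as CR in this way. The documents give no value for f. The apparent rate is 0.30 + 0.70f.

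| f | Apparent rate | P(X >= 13 of 28) |
|---|---|---|
| 0 | 0.300 | 0.049 |
| 2% | 0.314 | 0.069 |
| 5% | 0.335 | 0.107 |
| 10% | 0.370 | 0.200 |

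This shows how sensitive the cut-off is. It does not estimate what will happen.

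**The case against.** A reader might infer that a patient can be a complete responder on the day of entry. The documents do not support that. Section 11.21 requires all its conditions, including disappearance of all detectable clinical evidence of disease (11.211). Table 11.2 speaks of nodes regressing, and it also requires non-measured lesions absent, organs and marrow normal, and no new lesions. An unchanged node meets one component only.

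A reader might also infer that the whole response rate is biased upward. That goes too far as well. In the PET-CT column CR rests on the uptake score, with or without a residual mass. Extranodal lesions are unaffected, because CT-based CR requires no extralymphatic disease. Every assessed node must be at the boundary, and for the at-entry case that means exactly 1.5 cm with a short axis of 1.0 cm or less. Section 11.24 is also written for relapse and progression, not for baseline.

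Section 16.11 defines success as a confirmed response, and 11.1 schedules confirmatory scans. That would filter out some chance changes, but 16.3211 omits confirmation. It would not help for a node that was small throughout.

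The one- versus two-dimension difference carries little weight alone: 3.15 asks for measurable lesions, and the notes to Table 11.2 describe measured lesions as measurable in two diameters.

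What stands against these objections is that CT-only assessment is permitted, so PET cannot be relied on as the safeguard. Adopting a published classification also does not explain why 3.15 admits lesions already at its CR limit and then removes the only larger one.

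**Conclusion.** The overlap is real but narrow. For node-only disease read by CT alone, Section 3.15 guarantees no assessed node above the CR size limit, so the node-size component of CR can be met at entry. Whether CR itself is reached depends on the remaining conditions. PET-CT-based CR is not affected.

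The number of such patients cannot be derived from the documents, which give neither lesion sizes nor measurement error. Each one moves the rate by 3.6 points against a rule whose exact type I error is already 0.049. The higher error rates in the illustration hold only under the assumed shares. Small changes such as 1.6 to 1.5 cm are a property of the adopted CR rule, not evidence against the entry criterion. The change is worth making because it is a matter of wording and protects the primary endpoint.

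**What to change.** 1. **Section 3.15:** require at least two lesions, other than the one to be cryoablated, that are measurable in two perpendicular diameters and, if nodal, longer than 1.5 cm in longest diameter.
2. **Sections 11.0 and 11.221:** restrict target lesions to lesions of that kind.
3. **Table 11.2, 11.212 and 11.24:** reconcile the short-axis rule for nodes of 1.1 to 1.5 cm.
4. **Section 16.321:** add two analyses, labelled as sensitivity analyses only.
   - (a) Response rate counting as non-responders those CT-only complete responses in which all assessed nodes were within normal size at baseline.
   - (b) Response rate requiring an SPD fall of at least 50% for any CT-based complete response.

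Analysis (b) is needed because the amended 3.15 would still admit nodes of 1.6 or 1.8 cm. It adds a condition that the adopted criteria do not contain, so it should not replace the primary analysis. Nor should (a): it would count as a failure a small node that truly disappeared, and so would bias the rate downward. Both use diameters that the SPD assessment already calls for, and both can be specified for patients already enrolled.

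The cost is that a few patients with borderline nodes become ineligible and the sensitivity response rates may be slightly lower.
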